## 3 Study Design

### 3.1 General Overview

The TCD601B102 study is a 12-month, randomized, controlled, open-label, dose escalation study to evaluating safety, tolerability, pharmacokinetics and pharmacodynamics of an anti-CD2 monoclonal antibody, siplizumab, compared to anti-thymocyte globulin (rATG), as induction therapy in *de novo* renal transplant recipients. All subjects will receive background immunosuppression with standard exposure tacrolimus (TAC), mycophenolate mofetil (MMF) and corticosteroids (CS).

Up to 24 moderate immunological risk, *de novo* renal candidates will be enrolled into the study.

[figure not shown]

Figure 3-1 TCD601B102 Study Design

During the screening period (Day -28 to -1) and after informed consent has been signed, baseline subject information will be obtained in accordance with local regulations, including date of birth (month and year), age, sex (with childbearing status for females), race and ethnicity. In addition, relevant medical history (including CKD, ESRD and dialysis history) and current medical conditions at screening, a physical examination, vital signs, laboratory assessments, and a pregnancy test for female subjects of child-bearing potential will also be obtained.

[figure not shown]
Transplant procedures will also include information on the renal transplant procedure, recipient and donor transplant background, recipient and donor viral serology and recipient/donor HLA testing results.

Procedures performed prior to consent as part of medical standard of care may be considered in the determination of subject eligibility (e.g., HLA/ABO typing, laboratory results). Additionally, if the screening and study Day 0 visits occur in close proximity (i.e., within a 24-hour timespan), screening assessments are not required to be repeated.

Day 0 is defined as the day of transplant/day of first dose of study product. Upon confirmation of eligibility for the study, and no later than Day 0 (Day of Transplant), the subject will be randomized and assigned a treatment number within the electronic data capture (EDC) System/Interactive Web Response System (IWRS). Every effort should be made to randomize the subject on Day 0, but when logistical considerations prevent this from occurring (e.g., central pharmacy requirements), the subject may be randomized up to 24 hours pre-transplant.

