Eligible subjects will be sequentially assigned to one of two Cohorts (A or B) using a time-lagged dose escalation methodology as illustrated in Figure 3-2 below.

Figure 3-2 TCD601B102 Treatment Regimen

Background Immunosuppression (TAC/MMF/CS) will be administered with each treatment arm

Within each Cohort, it is planned that 12 subjects will be randomized between siplizumab (at two dose levels, increasing per Cohort as above) or rATG control, in an 8:4 ratio prior to renal transplantation on Study Day 0, as outlined in Table 3-1.

Table 3-1 **Dosing Regimen** 

Cohort	Arm	Subjects (n)	Product	Dosing Regimen
Cohort A	Arm 1	8	Siplizumab	0.2 mg/kg (Days 0 and 4)
	Arm 3	4	rATG	1.5 mg/kg (Day 0, 1 and 2)
Cohort B	Arm 2	8	Siplizumab	0.6 mg/kg (Days 0 and 4)
	Arm 3	4	rATG	1.5 mg/kg (Day 0, 1 and 2)

Subjects randomized to receive siplizumab will receive two intravenous (IV) doses on Days 0 and Day 4 post-transplant. The first dose will be administered intravenously, peri-operatively and must be completed prior to revascularization and perfusion of the allograft. The second and final dose of siplizumab will be administered intravenously on Day 4 post-transplant (Study Day 4). Subjects

randomized to the rATG control arm (Arm 3) will receive three intravenous (IV) doses of 1.5 mg/kg on Days 0, 1 and 2, regardless of Cohort assignment.

Siplizumab and rATG will be combined with concentration-controlled TAC (BID) dosing to a whole blood trough concentration 4-11 ng/mL, and MMF or equivalent (BID), and should be started within 24 hours post-transplant. Subjects will also receive CS per local practice with a minimum of 5.0 mg/d prednisone or equivalent until Month 12.

Dose escalation from one Cohort to the next will be determined 28 days following the last investigational product administration in the 4th siplizumab treated subject in each treatment Cohort and prior to dose escalation to the subsequent Cohort, a review of all available safety, tolerability and PD data will be conducted by ITB-MED in collaboration with the Investigators. This 28-day safety period allows sufficient time for subjects to reach full-receptor occupancy, maximum pharmacodynamic activity, and for the presentation of acute, drug related toxicities.

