# 4.5.4 Risk Mitigation Strategy

Safety and tolerability data for doses up to 15 mg/kg IV have been collected in patients with T-cell lymphoma with good tolerability. With initial administration of a biologic, the first 4 hours of exposure are most critical with most infusion reactions (including hypersensitivity, cytokine release, anaphylaxis) occurring within the first 2 hours of exposure (Tabrizi and Roskos 2007). No cytokine release has been detected with IV or s.c. siplizumab (MEDI-507) administration in the completed patient studies. Cytokine release or anaphylaxis have not been reported with similar compounds specifically targeting the CD2 receptor. A mild infusion reaction has been described in primates as well as clinical studies with siplizumab following the first dose. This first-dose-effect presents as mild and transient pyrexia with chills, nausea and fatigue. These infusion reactions are self-limiting and respond well to premedication with acetaminophen and diphenhydramine. Subjects will receive their first dose of siplizumab in the pre- to inter-operative time period, at a time when patients are under the close supervision of clinical staff in a hospital environment. Any infusion related reactions can be managed at that time in accordance with local protocols. In the TCD601B102 study all subjects will receive premedication prior to each dose of siplizumab to mitigate any infusion reactions.

Infections are a common risk for all transplant recipients. Subjects will be regularly evaluated while hospitalized and upon return to the clinic for signs and symptoms which might indicate a severe infection, i.e., fever, nausea, myalgia, headache, arthralgia, chills, diarrhea, stiff neck, and malaise, and will be treated as appropriate per local practice depending on the infectious agent. Subjects will be informed to report any of the aforementioned symptoms to the clinical staff to assure proper assessment and care can be administered in a timely manner.

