#### 6.2.6 **Siplizumab Administration**

Siplizumab will be administered by IV infusion to the subject by authorized site personnel on Day 0 and Day 4.

The first dose of siplizumab will be administered over an hour (±5 min) by IV infusion. The infusion should be administered pre- or intra-operatively and timed so that the completion of the infusion is no earlier than 4 hours prior to revascularization and perfusion of the allograft. When administered intra-operatively, the infusion must be completed prior to revascularization. This ensures both donor and alloreactive T-lymphocytes are suppressed and depletion is initiated in the hours and days post-transplant. The second and final dose will be administered by IV infusion over an hour on Day 4.

The compatibility of siplizumab with other IV medications is not known and must not be combined with other infusions or medications.

The infusion may be given directly into a peripheral vein or a separate lumen in an indwelling, multi-lumen, central catheter and not administered concurrently with any other medications.

The date, start time, completion time and volume of siplizumab administration must be recorded in the subject's source documentation and applicable eCRF.

For all subjects, regardless of the timing of the Day 0 infusion, the **Day 4 infusion** will be administered between 0800 and 1000 to facilitate future sample collection and study visits.

No dose adjustments beyond changes based on the subject's actual weight are permitted to the siplizumab dose during the study.

In case of notable AEs and/or SAEs, including loss of efficacy and/or associated PK/PD data collected during the study, changes to the next planned dose level across the study may be considered and implemented via a protocol amendment.

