#### 12.5.2 Safety Endpoints

For all safety analyses, the safety set will be used. All listings and tables will be presented by treatment group.

Safety summaries (tables, figures) include only data from the on-treatment period with the exception of baseline data which will also be summarized where appropriate (e.g., change from baseline summaries). In addition, a separate summary for death including on treatment and post treatment deaths will be provided. In particular, summary tables for AEs will summarize only on-treatment events, with a start date during the on-treatment period (treatment-emergent AEs).

The on-treatment period lasts from the date of first administration of study treatment through the month 12 or EOS visit.

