# Schedule of Assessments

### Footnotes

SCR = screening min = minute EOS/ET = end of study or early termination SD = noted in source document EOW = every other week Month = 28 days

☐ = Eligibility must also be confirmed on Day 0 prior to randomization

(a) all screening procedures may occur on the day of transplant for deceased donors

(b) vitals collected pre-dose, immediately following the end of the infusion, and 6 hours after completion of infusion with siplizumab or rATG. Other timepoints captured as indicated. Weight is captured pre-dose on Days 0 and 4 for siplizumab treated subjects and pre-dose on Days 0, 1 and 2 for rATG treated subjects.

(c) results obtained within the past 6 months acceptable; PRA when available

(d) results obtained within the past 12 months are acceptable for the initial assessment of EBV (donor and recipient) and CMV. Serological testing for BKV is not required at Screening. EBV, CMV and BKV viral testing via PCR should be conducted thereafter

(e) daily while in hospital and then as noted above; see protocol for panel analytes

(f) a negative pregnancy test must be available prior to randomization (for females of child bearing potential)

(g) DSA collected as noted above and additional collection with each kidney biopsy

(h) tacrolimus trough concentrations on days 0, 1, 7, 14, 21, 28; on months 3, 6, 12, and as clinically indicated. Sample Collection should be taken before the next dose is administered

(i) Randomization:

Subjects randomized to siplizumab: first dose administered pre-or intra-operatively and timed so that completion of the infusion is no earlier than 4 hours prior to revascularization and perfusion of the allograft. The Day 4 dose should be administered between 0800 and 1000 to faciliate future sample collection/visits.

Subjects randomized to rATG (Control): administration will occur on Day 0, Day 1 and Day 2 per SoC.

(j) must be started within 24 hours post-transplantion

(k) prophylaxis per local medical practice

(L) pre-implantation biopsy on Day 0; for-cause and/or protocol biopsies as indicated per local practice

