### **8.2. Definition of Baseline**

Unless otherwise stated, the last observed measurement prior to or on the date of first study medication will be considered the baseline measurement.

For eGFR analysis (See Section **Error! Reference source not found.**), the baseline will be based on the Week 4 assessment.

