#### **10.1.2. Adverse Events**

Each AE and SAE term will be recorded as a verbatim term on the case report forms (CRFs). All AEs and SAEs will be coded by primary system organ class (SOC) and mapped to a preferred term using the MedDRA dictionary (version 26.0 or higher). The investigator will assess AE severity and relationship to the study treatment.

All AEs will be listed. However, only treatment emergent adverse events (TEAEs) will be included in the AE summaries. A TEAE is defined as any AE with an onset date on or after the first study treatment dosing date. In addition, any AEs that the investigators deem to be treatment related, regardless of onset date, will also be considered TEAEs and will be included in the AE summaries.

For the purpose of calculating treatment emergence and inclusion in summary tables, incomplete onset dates will be imputed using the method described in Appendix A.

AEs will be summarized by the number and percentage of subjects in each primary SOC and preferred term. Subjects will be counted only once for each primary SOC and each preferred term. Summary tables of AEs by primary SOC, preferred term and severity will be provided. If a subject has more than one AE coded to the same preferred term, the subject will be counted only once for that preferred term by using the event with the highest severity. Similarly, if a subject has more than one AE within a primary SOC category, the subject will be counted only once in that SOC category by using the event with the highest severity. AEs by primary SOC, preferred term and relationship to study drug will be provided as well. If a subject has more than one AE coded to the same preferred term, the subject will be counted only once for that preferred term by using the most related event. Similarly, if a subject has more than one AE within a primary SOC category, the subject will be counted only once in that primary SOC category by using the most related event. In addition, serious adverse events (SAEs) by primary SOC and preferred term will be provided. Deaths and SAEs will be summarized similarly to AEs. All adverse event tables will also include the total number of events, counting multiple events per subject.

In the AE summary, preferred terms within each SOC will appear in alphabetical order.

Frequencies for deaths and hospitalizations will also be summarized by treatment group and overall.

All information obtained on AEs will be displayed by treatment group.

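### SAP 8.2 sets baseline by calendar date with no clock time, so a post-infusion Day 0 reading normally becomes the vital-sign baseline (and a post-dose laboratory value could)

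*SAP*

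**What the plan says.** SAP 8.2 gives the default rule: the "last observed measurement prior to or on the date of first study medication will be considered the baseline measurement". The only exception is eGFR, which uses Week 4. SAP 10.1.4 (vital signs) and 10.1.3 (laboratory) build change-from-baseline summaries and shift tables on this baseline without restating it.

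The first-dose date is fixed in Protocol 3.1: "Day 0 is defined as the day of transplant/day of first dose of study product". For that day, footnote (b) of the Schedule of Assessments has "vitals collected pre-dose, immediately following the end of the infusion, and 6 hours after completion of infusion with siplizumab or rATG".

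Protocol 6.2.6 sets the first siplizumab infusion at one hour (±5 minutes), "timed so that the completion of the infusion is no earlier than 4 hours prior to revascularization and perfusion of the allograft". Protocol 3.1 adds that the first dose "must be completed prior to revascularization and perfusion of the allograft". For rATG, Protocol 6.3.4 defers to the local label or the pharmacy manual and gives no infusion length.

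For chemistry and hematology, footnote (e) asks for daily samples in hospital and states no timing relative to the dose. Footnote (o), by contrast, fixes immunophenotyping as pre-dose on dosing days. Protocol 12.5.2 refers laboratory change to randomization/enrollment; SAP 10.1.3 replaces that with baseline.

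**The concern.** A baseline should describe the subject before treatment. Among several values dated Day 0, this rule takes the last, which is usually a reading made after the infusion and often after reperfusion.

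This conflicts with how the documents classify the same hours elsewhere. SAP 10.1.2 says: "A TEAE is defined as any AE with an onset date on or after the first study treatment dosing date". Protocol 12.5.2 says: "The on-treatment period lasts from the date of first administration of study treatment through the month 12 or EOS visit". A fever at the 6-hour reading would therefore be both a treatment-emergent event and that subject's baseline temperature.

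Clinically significant changes in vital signs, chemistry and hematology are listed under the primary objective in SAP 4.1. Protocol 4.5.4 describes "most infusion reactions (including hypersensitivity, cytokine release, anaphylaxis) occurring within the first 2 hours of exposure". The end-of-infusion reading, about 1 hour after the start, lies inside that window. If it becomes baseline, the change table cannot show the reaction as a rise from the pre-dose state.

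**Working it through.** The documents state no figure to reproduce. The check applies the SAP 8.2 rule literally to the Day 0 schedule.

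**Inputs.** Readings are at pre-dose, S + D and S + D + 6 h, where S is the start time and D the infusion length (Appendix 1, footnote b). For siplizumab D = 1 h (Protocol 6.2.6). There are 8 subjects per siplizumab arm, 16 in all. The distribution of S is not given, so two assumptions are shown.

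**Which reading is selected (siplizumab).**
- The 6-hour reading is dated Day 0 if S + 1 + 6 < 24, so S is before 17:00.
- The end-of-infusion reading is dated Day 0 if S + 1 < 24, so S is before 23:00.
- From 23:00 the pre-dose reading remains baseline.

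| Selected baseline | S uniform over 24 h | S uniform 06:00 to 18:00 |
|---|---|---|
| 6-hour reading | 17/24 = 70.8% (11.3 of 16) | 11/12 = 91.7% (14.7 of 16) |
| End of infusion | 6/24 = 25.0% | 1/12 = 8.3% |
| Pre-dose | 1/24 = 4.2% | 0% |
| Any post-infusion | 23/24 = 95.8% (15.3 of 16) | 100% |

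The ±5-minute tolerance moves these shares by less than 1 point (5/1440 = 0.3 points; 5/720 = 0.7 points).

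**Position relative to surgery.** Reperfusion is 0 to 4 h after the infusion ends. The 6-hour reading is therefore 6 - 4 = 2 h to 6 - 0 = 6 h after reperfusion, and about 7 h after the start of infusion.

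**Effect on the tables.** Let d be the selected reading minus the pre-dose reading. The reported change at any time is (value - pre-dose) - d. At the selected reading it is 0; at the pre-dose reading it is -d; every later visit is shifted by -d. If k of 8 subjects have deviation d, the arm mean change shifts by -(k/8) × d. For k = 1 to 4 (assumed deviations):
- d = +1.0 °C: -0.125 to -0.5 °C.
- d = -20 mmHg systolic: +2.5 to +10 mmHg.

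Shift tables likewise start from the post-infusion category.

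**rATG (D assumed).** A post-infusion baseline arises if S + D < 24.

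| D | S uniform over 24 h | S uniform 06:00 to 18:00 |
|---|---|---|
| 4 h | 20/24 = 83% | 100% |
| 6 h | 18/24 = 75% | 100% |
| 8 h | 16/24 = 67% | 10/12 = 83% |

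**Laboratory.** Daily in-hospital sampling can include Day 0, and nothing places that sample before the dose. A post-dose baseline is possible; the documents do not show how often it would occur.

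**The case against.** The wording and the clock arithmetic are hard to dispute; the objections concern size and reach.

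- **Most selected readings miss the reaction window.** In 71% to 92% of siplizumab subjects the baseline would be about 7 h after the start, outside the 2-hour window in Protocol 4.5.4. Protocol 4.5.1.1 says cytokine release may last several hours, but also that none has been reported with siplizumab. Reported infusion reactions were mild to moderate and transient, and subjects are premedicated. This stands as a limit on the likely size. It does not make a reading taken 2 to 6 h after reperfusion a pre-treatment value.
- **The percentages and deviations are assumptions.** This also stands. The conclusion itself needs only that the infusion ends before midnight and that the later Day 0 reading is recorded.
- **The term study medication is ambiguous.** SAP 10.1.1 also applies it to TAC, MMF and CS, and Protocol 6.4 allows pre-transplant immunosuppression. If that counted and began before Day 0, the rule would select an earlier value for that subject. This is a further reason to name the infusion.
- **The link to the primary endpoint is partial.** AE tables do not use this baseline, the vital-sign change and shift tables are SAP additions, and SAP 8.0 excludes hypothesis testing. All true; the affected tables still enter the final analysis as written.
- **A pre-dose reading may itself be intra-operative**, because the first dose may be given during surgery. This is correct, and changes from it may then include a surgical component. It still precedes the treatment under study.

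**Conclusion.** The point holds and should be fixed. It is a stated rule that gives the wrong value, because SAP 3 makes the approved plan binding for the final analysis. For siplizumab vital signs, a post-infusion baseline follows from the documents for every start before about 23:00, taking first study medication to mean the infusion and the scheduled readings to be present. The shares (95.8% or 100% post-infusion) rest on assumed start times, and the carry-over figures on assumed deviations. For rATG the same thing probably happens, but its infusion length is not given, so no difference between arms is claimed. For chemistry and hematology it is a possibility only.

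The damage is confined to the change and shift tables. AE tables, raw summaries by time and listings are unaffected, as are eGFR (Week 4 baseline) and immunophenotyping (pre-dose on dosing days).

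**What to change.** Replace the default in SAP 8.2 with: the last non-missing value collected before the start date and time of the first siplizumab or rATG infusion. Naming the infusion removes the ambiguity over TAC, MMF and CS.

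Add a rule for missing times: use the reading labelled pre-dose for vital signs and the Screening sample for laboratory values. Keep pre-dose Day 0 values eligible, because footnote (a) lets all screening for deceased-donor transplants take place on the day of transplant. Reconcile the reference point in SAP 10.1.3 with Protocol 12.5.2.

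The cost is SAP wording and programming; no new data are needed. Protocol 6.2.6 already requires siplizumab start times to be recorded. The documents do not say this for rATG, so the pre-dose label may be needed there.

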# 2 Objectives and Endpoints

Table 2-1 Objectives and Related Endpoints

Objective(s)	Endpoint(s)	
Primary Objective	Endpoints for primary objective	
To assess the safety, tolerability, PK and PD of siplizumab compared to rATG, in de novo renal transplant recipients at 12 months post-transplant.	
 
Adverse events
 
Serious adverse events
 
Clinically significant changes in clinical chemistry, hematology, vital signs, serology
 
siplizumab PK
 
Immunophenotyping
 
CD2 RO
 
eGFR via MDRD
 
	

 
Secondary Objectives
 
To measure changes in peripheral lymphocyte immunophenotype
 
To measure the time-course and duration of siplizumab induced lymphocyte depletion and time to recovery
 
To measure peripheral CD2-receptor occupancy following siplizumab administration over time
 
To assess the incidence of treated biopsy proven acute rejection (tBPAR) at 12 months
 
To assess the incidence of treatment emergent de novo, donor specific antibodies (DSA) at 12 months
 
To assess the incidence of antibody meditated rejection at 12 months
 
To assess repail function via eGER using MDRD equation at
 
	
 
Endpoints for secondary objectives
 
Immunophenotyping via FACS
 
Lymphocyte counts
 
CD2 RO
 
Anti-siplizumab Ab
 
Incidence of BPAR
 
de novo-DSA / anti-HLA antibody measurement
 
incidence of AMR
 
	

 
To assess renal function via eGFR using MDRD equation at Months 3, 6, 12 or EOS
 
		

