### 4. STUDY DESCRIPTION

#### 4.1. Study Objectives and Endpoints

Objectives	Endpoints
Primary	

To assess the safety, tolerability, pharmacokinetics (PK), and pharmacodynamics (PD) of siplizumab compared to rabbit anti-thymocyte globulin (rATG), in de novo renal transplant recipients over 12 months post-transplant.

	

Adverse events

Serious adverse events

Clinically significant changes in clinical chemistry, hematology, vital signs, serology

Siplizumab PK

PK-PD relationship

Secondary	

To measure changes in peripheral lymphocyte immunophenotype

To measure the time-course and duration of Siplizumab induced lymphocyte depletion and time to recovery

To measure peripheral CD2-receptor occupancy following Siplizumab administration over time

To assess the incidence of treated biopsy proven acute rejection (tBPAR) at 12 months

To assess the incidence of treatment emergent de novo, donor specific antibodies (DSA) at 12 months

To assess the incidence of antibody mediated rejection at 12 months

To assess renal function via eGFR using the Modification of Diet in Renal Disease (MDRD) equation at Months 3, 6, 12 or EOS

	

Immunophenotyping via FACS

Lymphocyte counts

CD2-receptor occupancy (RO)

Incidence of tBPAR

de novo DSA/anti-HLA antibody measurement

incidence of AMR

eGFR via MDRD

Exploratory

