## 5. INTERIM ANALYSIS

### 5.1. Interim Analysis Objectives

A formal interim analysis was conducted when 50% of subjects in Cohort 1 and 2 completed their 6-month study assessment according to a separate interim analysis plan (dated 03MAR2023). This formal interim analysis was conducted to assess the safety/tolerability (e.g., AEs, SAEs, clinical laboratory assessments, vital signs, PK data and PK/PD activity [e.g., immunophenotyping and CD2 receptor occupancy]). The analysis also included assessment of biopsy proven acute rejection (BPAR), graft losses deaths, and key safety endpoints. In the event the acute rejection rate exceeds a clinically relevant threshold set forth in the protocol and DMC charter, or the a priori defined stopping rules, enrollment were to be suspended to allow for the early termination of any treatment cohort where the benefit/risk of Siplizumab was deemed unacceptable.

The following treatment arms will be utilized for TCD601B102:

- Arm 1: Siplizumab 0.2 mg/kg (n=8 in Cohort A)
- Arm 2: Siplizumab 0.6 mg/kg (n=8 in Cohort B)
- Arm 3: rATG, a control arm, (n=4 each in Cohort A and B)

Subjects randomized to Siplizumab will receive two intravenous (IV) doses on Day 0 and Day 4 post-transplant and subjects randomized to rATG (Arm 3) will receive three intravenous (IV) doses of 1.5 mg/kg on Days 0, 1, and 2, regardless of Cohort assignment.

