### **8.4. Handling of Missing Values/Censoring/Discontinuations**

The following imputation method will be applied for subjects with missing data:

- Subjects who lose their graft will be assigned a value of zero for their missing estimated glomerular filtration (eGFR) value.
- Subjects who die or are lost to follow-up with a functioning graft will have an imputed value using the last-observation-carried-forward (LOCF) method.
- For subjects that discontinue randomized treatment, the eGFR will be considered missing after applying the windows.

Graft loss subjects do not have a functioning graft; hence the lowest possible GFR value (zero) will be assigned to such subjects. In contrast, subjects that die with a functioning graft, die for different reasons (e.g., suicide, car accident, cancer) will have an imputed value assigned as described above.

Subjects who are lost to follow-up have renal function, but missing values for various reasons (e.g., moving from the area or not being able to make the site visit during the Month 6 or Month 12 visit window).

Subjects who have a functioning graft at the time of death or are Lost to Follow-up with a functioning graft will be analyzed via an imputation method that employs LOCF.

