### 11.6. Renal Function

- **Change from baseline in renal function eGFR**

Renal function will be assessed by eGFR, using an automated calculation factoring serum creatinine, demographics and the MDRD4 formula.

MDRD 4-variable GFR Equation as below:

$$GFR \text{ in } mL/min \text{ per } 1.73 \text{ } m^2 = 175 \times \text{SerumCr}^{-1.154} \times \text{age}^{-0.203} \times 1.212 \text{ (if patient is black)} \\ * 0.742 \text{ (if female)}$$

- **Change from baseline in CKD-EPI**

The CKD-EPI equation are modeled using least squares linear regression to relate log transformed measured GFR to log-transformed filtration markers, age and sex with two slope splines for creatinine, Expressed as a single equation:

$$eGFR = 142 * \min(\text{standardized Scr/K, 1}) \alpha * \max(\text{standardized Scr/K, 1}) \\ - 1.200 * 0.9938 \text{Age} * 1.012 \text{ [if female]}$$

Abbreviations / Units:

*eGFR (estimated glomerular filtration rate) = mL/min/ 1.73 m^2*

*Scr (serum creatinine) = mg/dL*

*K = 0.7 (females) or 0.9 (males)*

*$\alpha = -0.241$  (females) or  $-0.302$  (males)*

*min = indicates the minimum of Scr/K or I*

*max = indicates the maximum of Scr/K or I*

The above parameters will be summarized by visit. This will also be evaluated at Months 3, 6 and 12 (EOS) by comparing the mean eGFR values between groups.

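### Does an eGFR baseline taken at Week 4, after all induction dosing, spoil the comparison of renal function between arms?

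*SAP*

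**What the plan says.** SAP 8.2 defines baseline in general as the last value up to the date of first study medication. For eGFR it makes an exception: "the baseline will be based on the Week 4 assessment". The section reference attached to that sentence has failed to resolve.

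On dosing, SAP 5.1 states that "Subjects randomized to Siplizumab will receive two intravenous (IV) doses on Day 0 and Day 4 post-transplant", and that rATG is given on Days 0, 1 and 2.

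SAP 11.6 opens with "Change from baseline in renal function eGFR", computed with the four-variable MDRD equation, and then lists the same for CKD-EPI. It goes on: "The above parameters will be summarized by visit". The next sentence reads "This will also be evaluated at Months 3, 6 and 12 (EOS) by comparing the mean eGFR values between groups".

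The objective is worded as a level at fixed times. SAP 4.1 has "To assess renal function via eGFR using the Modification of Diet in Renal Disease (MDRD) equation at Months 3, 6, 12 or EOS"; Protocol Section 2, Table 2-1, has "To assess renal function via eGFR using MDRD equation at Months 3, 6, 12 or EOS". Neither mentions change.

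For missing values, SAP 8.4 says "Subjects who lose their graft will be assigned a value of zero for their missing estimated glomerular filtration (eGFR) value".

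**The concern.** A baseline measured after randomised treatment is itself an outcome. If induction affects early graft function, the Week 4 value carries part of that effect, and subtracting it removes that part from every later change score. A lasting deficit would vanish, and a partly recovering one would appear as a gain. A graft lost before Week 4 could score zero minus zero, while the same loss afterwards would count in full.

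The timing makes this worth checking. Protocol 4.5.1.4 describes an early renal syndrome in two earlier siplizumab tolerance studies: creatinine rose from about Days 10 to 14, peaked between Days 10 and 20 and resolved by Day 30. Two of nine affected patients did not regain full function. That window runs up to Week 4. SAP 11.6 heads its renal items as change from baseline, and no visible text says that change ranks below the level comparison. A reader who set the change columns of the three arms side by side could conclude that they do not differ, or that the wrong arm did better.

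**Working it through.** **Timing.** Protocol Section 8 uses 7-day weeks, so Week 4 is Day 28. That is 28 - 4 = 24 days after the last siplizumab dose and 28 - 2 = 26 days after the last rATG dose. The baseline does follow all induction dosing in every arm.

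**What each summary measures.** Let D4 and D12 be the differences in mean eGFR between two arms at Week 4 and Month 12.

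- Difference in level at Month 12 = D12
- Difference in change from Week 4 = D12 - D4

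The level comparison contains no baseline term, so the choice of Week 4 cannot alter it.

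**Possible size.** The documents give no eGFR values, so all of these are assumed: 8 subjects per arm (SAP Section 8), k of them with a deficit d of 10 to 30 mL/min/1.73 m² at Week 4, and a fraction r recovered by Month 12. Compared with an uninjured arm:

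- Week 4 mean: -(k/8)·d
- Month 12 mean: -(k/8)·d·(1 - r)
- Mean change: +(k/8)·d·r

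| k | r | Week 4 mean | Month 12 mean | Mean change |
|---|---|---|---|---|
| 1 | 0 | -1.25 to -3.75 | -1.25 to -3.75 | 0 |
| 1 | 0.5 | -1.25 to -3.75 | -0.63 to -1.88 | +0.63 to +1.88 |
| 1 | 1 | -1.25 to -3.75 | 0 | +1.25 to +3.75 |
| 2 | 0 | -2.5 to -7.5 | -2.5 to -7.5 | 0 |
| 2 | 0.5 | -2.5 to -7.5 | -1.25 to -3.75 | +1.25 to +3.75 |
| 2 | 1 | -2.5 to -7.5 | 0 | +2.5 to +7.5 |

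Opposite signs need a deficit that is present at Week 4 and recovers in part afterwards. An injury resolved by Week 4 gives zero in all three columns. Wherever change misleads, the Week 4 mean shows why.

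**Sampling error.** Assume an SD of 15 to 20 and a correlation ρ between Week 4 and Month 12 of 0.3 to 0.8.

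- SE of a level difference = SD·√(2/8) = 7.5 to 10.0
- SE of a change difference = SD·√(2(1 - ρ))·√(2/8), from 15·√0.4·0.5 = 4.74 to 20·√1.4·0.5 = 11.83

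Every one-subject entry (at most 3.75) is below one SE. The largest two-subject entry (7.5) exceeds one SE of change only when the SE is near the low end of its range.

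**Graft loss.** Assume the other seven subjects go from 50 at Week 4 to 48 at Month 12. With one loss, the Month 12 mean is 7 × 48 / 8 = 42.0, whenever the loss happened. Mean change is:

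- loss before Week 4, zero at both visits: 7 × (-2) / 8 = -1.75
- loss before Week 4, subject left out of change: -2.00
- loss after Week 4: (-50 + 7 × (-2)) / 8 = -8.00

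The gap between the first and third is 50/8 = 6.25. It arises only if SAP 8.4 is read as also imputing a missing baseline, which it does not say. The visits it gives as examples are Months 6 and 12.

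**What the plan compares.** In SAP 11.6 the change parameters are summarised by visit. Between-group wording is attached only to mean eGFR at Months 3, 6 and 12, the same quantity as the objective. SAP 10.1.6 reports graft loss by group. SAP 10.1.3 summarises renal laboratory tests by visit, and SAP 10.1 presents safety variables by drug received. SAP 4.2.3 makes a non-technical graft loss in the first month a stopping event.

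**The case for a change.** The best case for a change is that nothing visible in SAP 11.6 ranks the two summaries. Change comes first under both headings, and the level comparison is introduced as something done *also*, with a loose pronoun that could be taken to refer back to change. The known early renal signal overlaps the baseline window, and a line of text would settle the matter at almost no cost.

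Part of this stands. The visible text gives change no supportive label, the treatment of a graft lost before Week 4 is not stated, and the cross-reference in 8.2 is broken. That reference may point to 12.4.1, an eGFR item in the exploratory section whose text is blacked out. If so, the Week 4 baseline applies only there, and 11.6 takes the pre-dose default. The level comparison is the same under either reading.

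The rest carries less weight. The sentence about groups speaks of mean eGFR values, not of changes. Harm requires a reader to build a contrast that the plan does not name and to pass over the one it does. Change from Week 4 is a fair description of the course after induction, in which partial recovery is a real gain; it misleads only if taken for a level. A pre-dose eGFR would be no better, since it reflects the recipient before the graft works. The earlier syndrome arose under a different conditioning regimen with marrow infusion, and Protocol 4.5.1.4 reports no such dysfunction in other siplizumab populations, including 13 renal transplant patients.

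**Conclusion.** The concern is right about the mechanism but calls for no change. Change from Week 4 should not be read as a treatment effect between arms: under the assumed deficits it could differ from the Month 12 contrast by as much as 7.5 mL/min/1.73 m², the full Week 4 deficit. The renal conclusion does not rest on it. The named comparison uses levels at Months 3, 6 and 12, agrees with the objective and scores a lost graft as zero. It does not depend on the baseline, although it still depends on the other missing-data rules in SAP 8.4.

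The gaps are of a kind that analysts fill sensibly. The broken reference is a clerical slip. Summaries by visit leave room for the Week 4 mean by arm, which would expose any early deficit. Whether a graft lost before Week 4 enters the change table is a table-footnote decision that leaves the Month 12 mean as it is. With 8 per arm and no hypothesis testing (SAP 8.0), no error rate is at stake.

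This rests on reading the between-group sentence in SAP 11.6 as a comparison of levels, which its words support, and on the visible text only. All eGFR values, SDs and correlations used here are assumed, so the size and direction of any real distortion are unknown.
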